8.2.3 Follow-up of AEs and SAEs

During the course of the study all AEs and SAEs should be proactively followed up for each patient. Every effort should be made to obtain a resolution for all events, even if the events continue after discontinuation/study completion.

Any AEs that are unresolved at the patient's last visit in the study are followed up by the investigator for as long as medically indicated, but without further recording in the eCRF.

AstraZeneca retains the right to request additional information for any patient with ongoing AE(s)/SAE(s) at the end of the study, if judged necessary. Adverse event data collection

'The following variables will be collect for each AE;

- AE (verbatim)
- The date and time when the AE started and stopped
- CTCAE grade 3 or more /Whether the AE is serious or not
- Investigator causality rating against the Investigational Product(s) (yes or no)
- Action taken with regard to Investigational Product(s)
- Select the appropriate as required: AE caused patient's withdrawal from study (yes or no)
- Outcome.

In addition, the following variables will be collected for SAEs:

- Date AE met criteria for serious AE
- Date Investigator became aware of serious AE
- AE is serious due to
- Date of hospitalisation
- Date of discharge
- Probable cause of death
- Date of death
- Autopsy performed
- Causality assessment in relation to Study procedure(s)
- Causality assessment to other medication'

8.2.4 Causality collection

The Investigator will assess causal relationship between Investigational Product and each Adverse Event, and answer 'yes' or 'no' to the question 'Do you consider that there is a reasonable possibility that the event may have been caused by the investigational product?'

For SAEs, causal relationship will also be assessed for other medication and study procedures. Note that for SAEs that could be associated with any study procedure the causal relationship is implied as 'yes'.

A guide to the interpretation of the causality question is found in Appendix B to the Clinical Study Protocol.

8.2.5 Adverse events based on signs and symptoms

All AEs spontaneously reported by the patient or care provider or reported in response to the open question from the study site staff: or revealed by observation will be collected and recorded in the CRF. When collecting AEs, the recording of diagnoses is preferred (when possible) to recording a list of signs and symptoms. However, if a diagnosis is known and there are other signs or symptoms that are not generally part of the diagnosis, the diagnosis and each sign or symptom will be recorded separately.

8.2.6 Adverse events based on examinations and tests

The results from the Clinical Study Protocol mandated laboratory tests and vital signs will be summarised in the CSR. Deterioration as compared to baseline in protocol-mandated laboratory values, vital signs should therefore only be reported as AEs if they fulfil any of the SAE criteria or are the reason for discontinuation of treatment with the investigational product.

If deterioration in a laboratory value/vital sign is associated with clinical signs and symptoms, the sign or symptom will be reported as an AE and the associated laboratory result/vital sign will be considered as additional information. Wherever possible the reporting Investigator uses the clinical, rather than the laboratory term (e.g., anaemia versus low haemoglobin value). In the absence of clinical signs or symptoms, clinically relevant deteriorations in non-mandated parameters should be reported as AE(s).

Deterioration of a laboratory value, which is unequivocally due to disease progression, should not be reported as an AE/SAE.

Any new or aggravated clinically relevant abnormal medical finding at a physical examination as compared with the baseline assessment will be reported as an AE unless unequivocally related to the disease under study, see sections 8.3.9 and 8.310.

Disease progression can be considered as a worsening of a patient's condition attributable to the disease for which the investigational product is being studied. It may be an increase in the severity of the disease under study and/or increases in the symptoms of the disease. The development of new, or progression of existing metastasis to the primary cancer under study should be considered as disease progression and not an AE. Events, which are unequivocally due to disease progression, should not be reported as an AE during the study.

New cancers

The development of a new cancer should be regarded as an SAE. New primary cancers are those that are not the primary reason for the administration of the study drug and have been identified after the patient's inclusion in this study.

Deaths

All deaths that occur during the study, or within the protocol-defined follow-up period after the administration of the last dose of study drug, must be reported as follows:

- Death clearly the result of disease progression should be reported to the study monitor at the next monitoring visit and should be documented in the eCRF but should not be reported as a SAE.
- Where death is not due (or not clearly due) to PD under study, the AE causing the death must be reported to the study monitor as a SAE within 24 hours. The report should contain a comment regarding the co-involvement of PD, if appropriate, and should assign main and contributory causes of death.
- Deaths with an unknown cause should always be reported as a SAE. A post mortem maybe helpful in the assessment of the cause of death, and if performed a copy of the post-mortem results should be forwarded to AstraZeneca/MedImmune Drug Safety or its representative within the usual timeframes.

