6.5 Concomitant therapy

Any medication or vaccine including over-the-counter or prescription medicines, vitamins, and/or herbal supplements that the patient is receiving at the time of enrolment or receives during the study must be recorded along with:

- Reason for use
- Dates of administration including start and end dates
- Dosage information including dose and frequency

Investigators may prescribe concomitant medications or treatments (eg, acetaminophen, diphenhydramine) deemed necessary to provide adequate prophylactic or supportive care except for those medications identified as "excluded" as listed below:

- Any investigational anticancer therapy
- Any concurrent chemotherapy, radiotherapy, immunotherapy, biologic, or hormonal
 therapy for cancer treatment. Concurrent use of hormones for non cancer-related
 conditions (eg, insulin for diabetes and hormone replacement therapy) is acceptable.
 - NOTE: Local treatment of isolated lesions, excluding target lesions, for palliative intent is acceptable (eg, by local surgery or radiotherapy).
- Immunosuppressive medications including, but not limited to systemic corticosteroids at doses beyond 10 mg/day of prednisone or equivalent; methotrexate, azathioprine, and tumour necrosis factor alpha blockers. Use of immunosuppressive medications in patients for the management of study drugrelated AEs or their use in patients with contrast allergies is acceptable. In addition, use of inhaled and intranasal corticosteroids is permitted.
- Live attenuated vaccines within 30 days of dosing. Inactivated viruses such as those in the influenza vaccine are permitted.

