Appendix B Adverse event definitions and additional safety information

B 1 **Definition of adverse events**

An adverse event is the development of any untoward medical occurrence in a patient or clinical study patient administered a medicinal product and which does not necessarily have a causal relationship with this treatment. An AE can therefore be any unfavourable and unintended sign (e.g. an abnormal laboratory finding), symptom (for example nausea, chest pain), or disease temporally associated with the use of a medicinal product, whether or not considered related to the medicinal product.

The term AE is used to include both serious and non-serious AEs and can include a deterioration of a pre-existing medical occurrence. An AE may occur at any time, including run-in or washout periods, even if no Study treatment has been administered.

B 2 Definitions of serious adverse event

A serious adverse event is an AE occurring during any study phase (i.e., run-in, treatment, washout, follow-up), that fulfils one or more of the following criteria:

- Results in death
- Is immediately life-threatening
- Requires in- patient hospitalisation or prolongation of existing hospitalisation
- Results in persistent or significant disability or incapacity.
- Is a congenital abnormality or birth defect
- Is an important medical event that may jeopardise the patient or may require medical treatment to prevent one of the outcomes listed above.

B3 Life threatening

'Life-threatening' means that the patient was at immediate risk of death from the AE as it occurred or it is suspected that use or continued use of the product would result in the patient's death. 'Life-threatening' does not mean that had an AE occurred in a more severe form it might have caused death (e.g., hepatitis that resolved without hepatic failure).

B4 Hospitalisation

Outpatient treatment in an emergency room is not in itself a serious AE, although the reasons for it may be (e.g., bronchospasm, laryngeal oedema). Hospital admissions and/or surgical operations planned before or during a study are not considered AEs if the illness or disease existed before the patient was enrolled in the study, provided that it did not deteriorate in an unexpected way during the study.

B 5 Important medical event or medical treatment

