Medical and scientific judgement should be exercised in deciding whether a case is serious in situations where important medical events may not be immediately life threatening or result in death, hospitalisation, disability or incapacity but may jeopardize the patient or may require medical treatment to prevent one or more outcomes listed in the definition of serious. These should usually be considered as serious.

Simply stopping the suspect drug does not mean that it is an important medical event; medical judgement must be used.

- Angioedema not severe enough to require intubation but requiring iv hydrocortisone treatment
- Hepatotoxicity caused by paracetamol (acetaminophen) overdose requiring treatment with N-acetylcysteine
- Intensive treatment in an emergency room or at home for allergic bronchospasm
- Blood dyscrasias (e.g., neutropenia or anaemia requiring blood transfusion, etc.) or convulsions that do not result in hospitalisation
- Development of drug dependency or drug abuse

B 6 For oncology studies, the following may be used instead:

The grading scales found in the revised National Cancer Institute CTCAE latest version will be utilised for all events with an assigned CTCAE grading. For those events without assigned CTCAE grades, the recommendation in the CTCAE criteria that converts mild, moderate and severe events into CTCAE grades should be used. A copy of the CTCAE can be downloaded from the Cancer Therapy Evaluation Program website (http://ctep.cancer.gov). The applicable version of CTCAE should be described clearly.

It is important to distinguish between serious and severe AEs. Severity is a measure of intensity whereas seriousness is defined by the criteria in Appendix B 2. An AE of severe intensity need not necessarily be considered serious. For example, nausea that persists for several hours may be considered severe nausea, but not a SAE unless it meets the criteria shown in Appendix B 2. On the other hand, a stroke that results in only a limited degree of disability may be considered a mild stroke but would be a SAE when it satisfies the criteria shown in Appendix B 2.

B 7 A Guide to Interpreting the Causality Question

When making an assessment of causality consider the following factors when deciding if there is a 'reasonable possibility' that an AE may have been caused by the drug.

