Appendix D: Recommended Treatment Modifications for Durvalumab and Management Recommendations

Adverse Reactions	Severity ^a	DURVALUMAB Treatment Modification	Corticosteroid Treatment Unless Otherwise Specified
Immune-mediated pneumonitis	Grade 2	Withhold dose ^b	Initiate 1 to 2 mg/kg/day prednisone or equivalent followed by a taper
	Grade 3 or 4	Permanently discontinue	1 to 4 mg/kg/day prednisone or equivalent followed by a taper
Immune-mediated hepatitis	Grade 2 with ALT or AST >3- 5xULN and/or total bilirubin >1.5- 3xULN Grade 3 with AST or ALT ≤8xULN or total bilirubin ≤5xULN	Withhold dose ^b	Initiate 1 to 2 mg/kg/day prednisone or equivalent followed by a taper
	Grade 3 with AST or ALT >8xULN or total bilirubin >5xULN Concurrent ALT or AST >3xULN and total bilirubin >2xULN with no other cause	Permanently discontinue	
Immune-mediated colitis or diarrhea	Grade 2	Withhold dose ^b	Initiate 1 to 2 mg/kg/day prednisone or

Adverse Reactions	Severity ^a	DURVALUMAB Treatment Modification	Corticosteroid Treatment Unless Otherwise Specified
	Grade 3 or 4	Permanently discontinue	equivalent followed by a taper
Immune-mediated endocrinopathies: Hyperthyroidism	Grade 2-4	Withhold dose until clinically stable	Symptomatic management
Immune-mediated endocrinopathies: Hypothyroidism	Grade 2-4	No changes	Initiate thyroid hormone replacement as clinically indicated
Immune-mediated endocrinopathies: Adrenal insufficiency, Hypophysitis/hypopituitarism	Grade 2-4	Withhold dose until clinically stable	Initiate 1 to 2 mg/kg/day prednisone or equivalent followed by a taper and hormone replacement as clinically indicated
Immune-mediated endocrinopathies: Type 1 diabetes mellitus	Grade 2-4	Withhold dose until clinically stable	Initiate treatment with insulin as clinically indicated
Immune-mediated nephritis	Grade 2 with serum creatinine >1.5-3x (ULN or baseline)	Withhold dose ^b	Initiate 1 to 2 mg/kg/day prednisone or equivalent followed by a taper
	Grade 3 with serum creatinine >3x baseline or >3-6xULN; Grade 4 with serum creatinine >6xULN	Permanently discontinue	
Immune-mediated rash or dermatitis	Grade 2 for >1 week	Withhold dose ^b	Initiate 1 to 2 mg/kg/day prednisone or equivalent followed by a taper
	Grade 3 Grade 4	Permanently discontinue	
Immune-mediated myocarditis	Grade 2	Withold dose ^c	Initiate 2 to 4 mg/kg/day prednisone

Adverse Reactions	Severity ^a	DURVALUMAB Treatment Modification	Corticosteroid Treatment Unless Otherwise Specified

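### Protocol 8.2.6, read literally, leaves a non-serious, asymptomatic liver or renal laboratory deterioration that leads only to dose withholding outside AE recording; other passages point the other way, and no planned SAP table would show such cases

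*Protocol*

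**What the plan says.** **The recording rule.** Protocol Section 8.2.6 notes that mandated laboratory results and vital signs will be summarised in the study report, and concludes that deteriorations in them "should therefore only be reported as AEs if they fulfil any of the SAE criteria or are the reason for discontinuation of treatment" with the study drug. Its next paragraph makes the symptom the AE when there is one. For silent changes it adds: "In the absence of clinical signs or symptoms, clinically relevant deteriorations in non-mandated parameters should be reported as AE(s". Section 8.1.1 sends the reader to 8.2.6 for laboratory AEs. Later in 8.1.1 a second pointer goes to Section 6.4.3, which this protocol does not contain.

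**The events.** Appendix D lists immune-mediated hepatitis and nephritis as adverse reactions and grades them by laboratory values. The rows that call for withholding the dose include "Grade 3 with AST or ALT ≤8xULN or total bilirubin ≤5xULN" and "Grade 2 with serum creatinine >1.5-3x (ULN or baseline". ALT, AST, total bilirubin and creatinine are all in the mandated chemistry panel of 8.1.1.

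**Text pointing the other way.** In Section 8.2.5, "the recording of diagnoses is preferred (when possible) to recording a list of signs and symptoms". Appendix B 1 says: "An AE can therefore be any unfavourable and unintended sign (e.g. an abnormal laboratory finding". Appendix B 5 treats as usually serious an event that "may require medical treatment to prevent one or more outcomes listed in the definition of serious". Section 6.5 says that immunosuppressive medication "for the management of study drugrelated AEs or their use in patients with contrast allergies is acceptable". Section 6.6 names hepatitis among the potential immune-related AEs.

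**The planned summary.** SAP Section 6.3.1 does not describe laboratory analysis. The shells for Tables 14.3.4.1 to 14.3.4.4 count normal and abnormal results by visit, and split abnormal ones by investigator-judged clinical significance.

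**The concern.** The primary endpoint is the number and proportion of patients with AEs, SAEs and AEs of special interest. Liver and renal immune-mediated events are among those the study is meant to detect: the synopsis names hepatitis for close monitoring, and Section 4.2 supports the 141-day treatment phase with median onset times that include hepatitis (70 days) and nephritis (91 days). Yet 8.2.6 does not list a withheld dose as a reason to record an AE. If one site applies the word only in 8.2.6 and another enters the diagnosis, the same event counts at one site and not at the other. The restriction would be tolerable if the laboratory summary it relies on could show what was left out. As planned, it cannot.

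**Working it through.** **1. The plan's own figure.** The only sample-size calculation is for an AE proportion of 31% with a precision of 10 points: n = 1.96² × 0.31 × 0.69 / 0.10² = 82.17, rounded up to 83 as stated. At 100 patients the half-width is 1.96 × √(0.31 × 0.69 / 100) = 9.06 points. The point does not depend on this figure, but it gives a scale.

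**2. The test case against 8.2.6.** Take a silent, non-serious rise in ALT, AST, bilirubin or creatinine after which a dose is withheld and treatment later resumes.

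| Route to an AE in 8.2.6 | Does the case qualify? |
|---|---|
| Meets an SAE criterion | No, non-serious by assumption |
| Reason for discontinuing study drug | No, withheld only |
| Associated sign or symptom | No, asymptomatic |
| Silent but clinically relevant deterioration | No, this covers non-mandated tests only |

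No route is met.

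**3. The test case against the other passages.** A site that diagnoses hepatitis or nephritis has a reason to record it under 8.2.5, 6.6 and Appendix D. A site that starts a corticosteroid relies on the 6.5 exception, which assumes a drug-related AE. Appendix B 5 may make the event serious by judgement, which then meets the first trigger in 8.2.6. SAP Table 14.2.1.2 has a row for AEs with temporary interruption of the product. So the passages conflict, and the case most likely to go unrecorded is one with no diagnosis entered and no corticosteroid started.

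**4. What the SAP tables would show.**
- There is no CTCAE grade, multiple of the upper limit of normal, worst post-baseline value or shift from baseline. Counts are by analyte and visit, so they cannot be matched to an Appendix D row or to an AE record.
- Table 14.3.4.2 has creatinine clearance but no serum creatinine, on which the nephritis rows rest. Under the 8.1.1 footnote, clearance is tested every 4 weeks: Days 1, 29, 57, 85, 113 and 141, or 6 of the 11 tabulated visits (Visits 2 to 12). Chemistry, including renal function, is scheduled at all 11, so the data should exist and the table omits them.
- Listing 16.3.5.2 has no reference-range column, although laboratories are local.

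**5. Illustration of size.** The documents give no rate of such events. Let e be the share of patients with an unrecorded event and q the independent share with any other AE. The any-AE proportion then loses 100 × e × (1 − q) points. With e assumed at 1% to 5%:
- q = 31% (the planning value): 0.69 to 3.45 points
- q = 60% (assumed): 0.40 to 2.00 points
- q = 90% (assumed): 0.10 to 0.50 points

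An event-specific count is not diluted in this way. With invented counts, 1 missed of 5 true cases is 20%, 2 of 5 is 40%, and 1 of 2 is 50%.

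**The case against.** The strongest reply is that 8.2.6 governs laboratory values, not diagnoses. In Appendix D the values stand under severity and grade a reaction already identified, so a site using such a row has already recognised an adverse reaction. The withhold rows for hepatitis and nephritis also call for corticosteroids, which 6.5 ties to drug-related AEs. This largely stands. A reader might infer that Appendix D defines hepatitis and nephritis by laboratory values alone, so that every silent case, treated or not, is lost. The documents do not support that.

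A reader might also infer that the reference to Section 6.4.3 leaves sites without guidance. It does not: 8.1.1 also points correctly to 8.2.6, and the other reference is stale. Nor is renal function checked only every 4 weeks; that interval applies to creatinine clearance.

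The records also offer a cross-check. Section 6.6 requires the reasoning for dose modifications to be documented, 6.4 puts interruptions in the eCRF, 6.5 asks the reason for each concomitant medication, and Listing 16.1.8 has an indication column. This stands too, but it works patient by patient, and no planned table uses it.

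Finally, any loss in the any-AE proportion is probably small beside a half-width of about 9 points in a study without hypothesis tests, and pneumonitis is the only AE of special interest the endpoint names. That limits the weight of the point. It does not resolve the conflict: none of the counter-passages overrides the explicit restriction in 8.2.6, and a bias towards undercounting is not covered by a confidence interval.

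**Conclusion.** The point holds in a narrow form. A non-serious, asymptomatic deterioration in a mandated liver or renal test that leads only to withholding meets no trigger in 8.2.6, while several other passages favour recording it. The likely result is inconsistent recording and some undercount, not the loss of all such events. Its size is unknown: the 1% to 5% share and the 20%, 40% and 50% figures are illustrations. The clearer defect is in the SAP, where the summary that 8.2.6 relies on cannot show how many laboratory elevations lie outside the AE tables. This is an inexpensive improvement to the reporting. It does not make the primary endpoint uninterpretable. Confidence is moderate, because the effect depends on how sites read the conflicting text.

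**What to change.** Before database lock:

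1. **Laboratory tables.** Add patient-level tables of worst post-baseline CTCAE grade and of shift from baseline to worst value for ALT, AST, total bilirubin and serum creatinine. State one CTCAE version: Section 6.6 and Appendix D use 4.03, while Appendix B 6 refers to the latest. Add a serum creatinine row to Table 14.3.4.2 and reference ranges to Listing 16.3.5.2. First confirm that ranges are held for scheduled samples, because the sentence on them in 8.1.1 follows one about additional samples.
2. **Threshold counts.** Count patients reaching the laboratory thresholds that Appendix D uses. Label these as elevations of any cause, not as immune-mediated hepatitis or nephritis, and keep them separate from the AE count. State how many of these patients have no matching AE, using the dosing and concomitant-medication listings for context.
3. **Protocol text.** Reconcile 8.2.6 with 8.2.5, Appendix B and Appendix D on what is recorded as an AE, and correct the Section 6.4.3 reference. If the recording rule changes during the trial, document the date and look for earlier events in the existing records.

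The cost of items 1 and 2 is extra programming. They need no new patient procedures, and the reported rate of laboratory events may rise somewhat. Item 3 needs ethics committee approval and would come late: version 4.1 is dated 12 October 2022 and last patient in was estimated for Q4 2022. The SAP changes are therefore the safer first step.
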